1.3 Schedule of Assessments

Table 1: Schedule of Assessments

Procedures	Scr ¹	Intervention Period (Study Month)															EOS ²
Study Month	N/A	M0			M1	M2	M3	M4	M5	M6	M7	M8	M9	M10	M11	M12/ ET ³	M15
Nominal Study Day	-30 ¹	D1 Pre infusion	D1 Post infusion	D8	D30	D60	D90	D120	D150	D180	D210	D240	D270	D300	D330	D360	D450
Visit allowance (±days)		N/A	N/A	±3	±7	±7	±7	±7	±7	±7	±7	±7	±7	±7	±7	±7	±7
Study Visit	N/A	1		2	3	4	5	6	7	8	9	10	11	12	13	14	15
Informed consent	x																
Inclusion/exclusion criteria review	x	x															
Medical history	x																
Review of kidney biopsy ⁴	x																
Physical examination ⁵	x																x
Weight	x	x								x			x			x	x
Vital signs ⁶	x	x	x	x	x	x	x	x	x	x	x	x	x	x	x	x	x
12-lead ECG	x																
Randomization		x															
Study intervention infusion ⁷		x			x	x	x	x	x	x	x	x	x	x	x		
AE monitoring	x	x	x	x	x	x	x	x	x	x	x	x	x	x	x	x	x
Concomitant medications review	x	x	x	x	x	x	x	x	x	x	x	x	x	x	x	x	x
HBV, HCV, HIV serology	x																
Serum β-hCG (females only)	x																
Urine β-hCG (females only)		x			x	x	x	x	x	x	x	x	x	x	x	x	x
Serum chemistry ⁸	x	x			x	x	x	x	x	x	x	x	x	x	x	x	x
Hematology ⁹	x	x					x			x				x		x	x

Procedures	Scr ¹	Intervention Period (Study Month)															EOS ²
	N/A	M0			M1	M2	M3	M4	M5	M6	M7	M8	M9	M10	M11	M12/ ET ³	M15
Nominal Study Day	-30 ¹	D1 Pre infusion	D1 Post infusion	D8	D30	D60	D90	D120	D150	D180	D210	D240	D270	D300	D330	D360	D450
Visit allowance (±days)		N/A	N/A	±3	±7	±7	±7	±7	±7	±7	±7	±7	±7	±7	±7	±7	±7
Study Visit	N/A	1		2	3	4	5	6	7	8	9	10	11	12	13	14	15
Urinalysis (dipstick and microscopy) ¹⁰	x	x		x	x	x	x	x	x	x	x	x	x	x	x	x	x
24-hour urine collection ¹¹	x												x			x	x
Urine sample for uPCR determination	x ¹²	x		x	x	x	x	x	x	x	x	x	x ¹²	x	x	x ¹²	x ¹²
Urine sample for uACR determination	x ¹²												x ¹²			x ¹²	x ¹²
Blood sample for lymphocytes		x								x						X	x
Serum for PK ¹³		x	x	x	x ¹⁴	x ¹⁴	x ¹⁴	x ¹⁴	x ¹⁴	x ¹⁴	x ¹⁴	x ¹⁴	x ¹⁴	x ¹⁴	x ¹⁴	x	x
Blood for total IgA, IgG, and IgM ¹³	x	x	x	x	x	x	x	x	x	x		x	x	x	x	x	x
Blood for IgA subtypes		x					x			x			x			x	x
Serum for APRIL ¹		x	x		x	x	x ¹⁴	x	x	x ¹⁴	x	x	x ¹⁴	x	x ¹⁴	x	x
Serum for a-g IgA ₁ and anti-IgA ₁	x	x					x			x			x			x	x
Serum for ADA ¹⁵		x			x	x		x		x		x			x	x	x
Blood sample for DNA ¹⁶		x															
Urine sample for exploratory biomarker assessments ¹⁷		x					x			x			x			x	x
Blood for markers of complement activity ¹³		x								x						x	

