- ⁷ The dose of study intervention will be based on the M0 predose weight.
- ⁸ The comprehensive list of serum chemistry tests to be performed is provided in [Appendix 2](#). A full serum chemistry panel will be obtained at screening and on M0, M3, M6, M9, M12, and M15; the following tests are required at other visits: sodium, potassium, chloride, bicarbonate, blood urea nitrogen, creatinine, and glucose. Local laboratory assessments may be performed at Investigator discretion throughout the study in the course of patient care (but not assessments that would potentially unblind treatment status, such as measurement of immunoglobulin levels). Any clinically significant abnormalities should be recorded in the eCRF.
- ⁹ The comprehensive list of hematology tests to be performed is provided in [Appendix 2](#).
- ¹⁰ The comprehensive list of urinalysis tests to be performed is provided in [Appendix 2](#). On days of 24-hour urine collection, the uPCR sample will be collected from the 24-hour urine collection and routine urinalysis will be performed on a sample freshly voided during the clinic visit.
- ¹¹ Participants will discard the first void and begin a 24-hour urine collection the day prior to the clinic visit. For all 24-hour urine collection, the following parameters will be obtained or derived: 24-hour urine volume, protein, albumin, and creatinine, uPCR, and uACR.
- ¹² Samples should be taken from the 24-hour urine sample.
- ¹³ Up to 60 participants (approximately 15 per cohort) may have a more extensive PK and PD sampling schedule, as described in [Table 5](#). Study participants agreeing to participate in this more intensive PK and PD sample collection sub-study will sign an additional informed consent for this activity.
- ¹⁴ Blood samples to be collected before and after study intervention infusion at all visits.
- ¹⁵ Samples for ADA assessment will be collected before the start of infusion.
- ¹⁶ Samples for evaluation of host genetic markers related to IgAN susceptibility loci, the APRIL/BAFF pathway, and/or immunity will be collected before the start of infusion.
- ¹⁷ On days of 24-hour urine collection, urine samples for exploratory biomarker analysis will be collected and stored from a sample freshly voided during the clinic visit.

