2.3 Benefit/Risk Assessment

2.3.1 Risk Assessment

Table 2 summarizes the important potential risks that have been recognized during the conduct of VIS649 nonclinical and clinical development programs. At present, all are considered potential risks.

More detailed information about the risks and reasonably expected adverse events (AEs) of VIS649 may be found in the Investigator's Brochure.

Table 2: Summary of Potential Risks Associated with VIS649

Potential Risk of Clinical Significance	Summary of Data/Rationale for Risk	Mitigation Strategy
IgA suppression risk	
Based on the mechanism of action of VIS649, preclinical studies, and human data from healthy volunteers, total serum IgA levels are expected to be suppressed to nadir levels [REDACTED].
 
There is increasing recognition that selective IgA deficiency, which has typically been associated with IgA levels below the lower limit of detection [REDACTED], may be associated with recurrent sinopulmonary infection, allergy, autoimmunity, and gastrointestinal microbiome perturbation (Yazdani, Azizi et al. 2017, Fadlallah, El Kafsi et al. 2018).
 
VIS649 is expected to reduce but not ablate IgA expression. Additionally, the syndrome of selective IgA deficiency is often associated with additional immunologic impairments, including T-cell disorders which are not expected to occur with VIS649 dosing.
	
 Serum IgA, IgG, and IgM will be measured on a monthly basis (as blinded data, to be made available for routine DSMB review). The DSMB will assess unblinded safety data on a scheduled and ad hoc basis as needed, including AEs, laboratory data and Ig data. The DSMB charter calls for assessment of the relationship of AEs to observed Ig levels (IgA, IgG and IgM) in study participants. If needed, the DSMB charter also calls for specific risk-mitigation strategies including, but not limited to, change in inclusion/exclusion criteria, establishing criteria for stopping study intervention in a participant or a cohort,

Potential Risk of Clinical Significance	Summary of Data/Rationale for Risk	Mitigation Strategy
	
Additional information can be found in the Investigator’s Brochure.
	
establishing criteria for rescue therapies such as IVIG and change in dosing schedule of a participant or a cohort based on standardized safety lab analysis and AE analysis.

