	
increased risk of auto-immune diseases(Yel, Ramanuja et al. 2009, Louis and Gupta 2014, Louis, Agrawal et al. 2016, Janssen, Macken et al. 2018). Selective IgM deficiency is usually associated with other defects such as decreased T-helper cell activity, increased isotype specific suppressor T cells, increased CD8 Treg cells, and intrinsic B cell defects.
 
VIS649 is not expected to have effects such as these on cellular immunity.
	

Nonspecific immunosuppression risk
	
There is the possibility of nonspecific immunodeficiency with potential risk of exacerbation of pre-existing latent infection or poor response to new infection.
 
Additional information can be found in the Investigator’s Brochure.
	
 • Participants with acute or chronic infections at the time of screening are prohibited from enrollment. • Participants with underlying iatrogenic or primary immunodeficiency syndromes are prohibited from enrollment. • DSMB monitoring will include careful attention to infection-related AEs. • Concurrent treatment with systemic corticosteroids or other immunosuppressive therapy is prohibited during study conduct.

Infusion reactions (anaphylaxis, fever, chills, rigors, nausea, vomiting, pain, headache, dizziness, shortness of breath, bronchospasm, hypotension, hypertension, pruritus, rash, urticaria, angioedema, diarrhea, tachycardia, and chest pain)
	
There was no effect of VIS649 on measured plasma cytokine concentrations in the monkey toxicology studies, and VIS649 did not stimulate significant cytokine release in an in vitro human peripheral blood lymphocyte cytokine release assay. There were no SAEs attributable to VIS649 among participants in the Phase 1 VIS649-101 study at dose levels up to 12 mg/kg.
 
Severe infusion reactions such as anaphylaxis have not been observed with VIS649 in humans.
 
Additional information can be found in the Investigator’s Brochure.
	
 • All VIS649 doses will be administered at the clinical site by trained personnel, and participants will be closely monitored for the occurrence of infusion reactions.

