The study will evaluate 3 dose levels of VIS649 (2, 4, and 8 mg/kg) versus placebo. A total of 144 participants will be randomized with equal allocation (1:1:1:1) across the 4 intervention groups (approximately 36 participants per group). Randomization will be stratified first by region (Japan vs rest-of-world). A target of twelve or more participants are planned to be randomized in Japan; these participants will be randomized with equal allocation and without

further stratification. The randomization for the rest-of-world will be stratified by screening uPCR (≤ 2.0 g/g vs > 2.0 g/g).

VIS649 or placebo will be administered as twelve-monthly IV infusions starting on Day 1. Participants will return to the study center on Day 8 and then monthly through Month 12 for safety, PK and/or PD assessments. Participants will be encouraged to follow the schedule of visits for their monthly infusions as close to the prescribed interval as possible. If under special circumstances, a participant is unable to visit the study center within 7 days of the schedule infusion they may still be able to receive the infusion within the next 7 days, and this will be recorded as a protocol deviation. However, if there is any further delay, that dose should be skipped, and the participant should receive subsequent doses as per the schedule. The participant will not receive additional doses to make up for the missed dose.

Safety assessments will include review of AEs (including hypersensitivity reaction and anaphylactic reaction), physical examinations, injection site tolerability (including pain, irritation and tissue damage), clinical laboratory assessments (including biochemistry, hematology, and urinalysis), laboratory testing including serum Ig levels, vital sign measurements, and use of concomitant medications.

Participants will return to the study center on Month 15, approximately 120 days following the last dose of study intervention (Dose 12) for additional safety, PK, PD, and efficacy assessments. Participants discontinuing dosing prior to Dose 12 will attend an early termination visit at the time of dosing discontinuation and will be encouraged to attend the study visits as per schedule of assessments (Table 1).

An independent DSMB will review safety data at regular intervals (see Section 9.6).

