5.2 Exclusion Criteria

Participants are excluded from the study if they meet any of the following criteria:

1. Participant has secondary forms of IgAN as defined by the treating physician (eg,, Henoch-Schönlein purpura, minimal change disease with IgA deposits, infection associated IgAN or IgAN associated with hepatic cirrhosis).
2. Participant has co-existing CKD, other than IgAN.
3. Participant has evidence of additional pathological findings in the kidney biopsy (eg, diabetic kidney disease, membranous nephropathy or lupus nephritis lupus). However, hypertensive vascular changes are acceptable.
4. Participant has kidney biopsy MEST or MEST-C score of T2 or C2 from the Oxford IgAN classification schema. If MEST-scoring was not performed, the presence of $> 50\%$ tubule-interstitial fibrosis or crescents in $> 25\%$ of glomeruli is exclusionary.
5. Participant has nephrotic syndrome, defined for this purpose as 24-hour urine protein > 3.5 g with concurrent hypoalbuminemia (serum albumin < 2.5 g/dL), hyperlipidemia (total cholesterol > 350 mg/dL) and edema.
6. Participant has received a solid organ transplant, including kidney.
7. Participant has received bone marrow or hematologic stem cell transplantation.
8. Participant is currently receiving systemic immunosuppression (excluding topical, ophthalmic, per rectum or inhaled corticosteroids).
9. Participant has received systemic steroids within the 12 weeks prior to initial screening.
10. Participant has received treatment with 2 or more systemic immunosuppressive agents within 2 years prior to initial screening.
11. Participant has chronic infectious diseases (eg, chronic urinary tract infection, chronic sinusitis, bronchiectasis, active pulmonary or systemic tuberculosis, chronic viral HCV or hepatitis B virus or HIV infection).

12. Participant has a known allergy or intolerance to any component of the study intervention.
13. Participant has acute infectious disease at the time of screening. Participants may be rescreened following resolution of acute infection (such as urinary tract infection or respiratory tract infection), provided there is no evidence of an immunosuppressive condition that predisposed the participant to this infection.
14. Participant has Type 1 diabetes.
15. Participant has uncontrolled Type 2 diabetes, as evidenced by a screening hemoglobin A1c value > 8%.
16. Participant has uncontrolled blood pressure (> 160 mm Hg systolic or > 110 mm Hg diastolic).

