8.6 Pharmacodynamics

Serial blood samples will be drawn in order to determine serum IgA, IgG, and IgM concentrations as well as the following analytes for exploratory PD endpoints [REDACTED]

[REDACTED] Up to 60 participants (approximately 15 participants in each cohort) will have a more intensive total serum IgA/IgM/IgG sampling schedule, as described in Table 5. Study participants who agree to participate in this more intensive sample collection sub-study will sign an additional informed consent for this activity.

It is expected that VIS649 will result in obvious reductions in serum IgA and IgM, which, if visible to site and Sponsor staff at the participant level, would effectively unblind treatment assignment. Participant level unblinded Ig data will not be available for review by the site or Sponsor staff. Unblinded Ig data will be routinely reviewed by the DSMB as part of the scheduled, if required, ad hoc safety reviews (see Section 9.6). Additional PK/PD summaries will be provided at an aggregate level in accordance with planned interim analyses (see Section 9.5).

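### Two mitigations stated in Protocol Table 2 do not match the operative text: Table 1 has no Month 7 immunoglobulin draw, and no criterion in Section 5.2 names primary immunodeficiency

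*Protocol*

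**What the plan says.** **Ig monitoring.** In the IgA row of Table 2 (Protocol 2.3.1) the first mitigation reads "Serum IgA, IgG, and IgM will be measured on a monthly basis (as blinded data, to be made available for routine DSMB review". The IgG and IgM rows refer back to it. Table 1 (Protocol 1.3) sets the draws for all participants in its row "Blood for total IgA, IgG, and IgM". Table 5 (Protocol 8.5) lists a pre-infusion Ig sample for Months 4 to 10. Section 8.6 ties the Table 5 Ig sampling to a subset of up to 60 who "will have a more intensive total serum IgA/IgM/IgG sampling schedule, as described in Table 5" and who sign an additional consent. Table 1 footnote 13 describes the same subset: "Up to 60 participants (approximately 15 per cohort) may have a more extensive PK and PD sampling schedule".

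**Immunodeficiency.** Under nonspecific immunosuppression risk, Table 2 states: "Participants with underlying iatrogenic or primary immunodeficiency syndromes are prohibited from enrollment". The criteria that sites apply are in Sections 5.1 and 5.2. The nearest exclusion is number 8: "Participant is currently receiving systemic immunosuppression (excluding topical, ophthalmic, per rectum or inhaled corticosteroids". Exclusions 9 and 10 deal with recent steroids and earlier immunosuppressive agents. Inclusion 6 requires IgG of at least 700, IgM of at least 40 and IgA of at least 70 mg/dL.

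**The concern.** Table 2 explains how known risks are contained, but sites take samples from Table 1 and enroll from Section 5. Where the two differ, a site that follows the protocol exactly does not deliver what Table 2 describes.

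For Ig, the site cannot close the gap itself. Table 1 footnote 8 rules out local Ig measurement because it could unblind, and Section 6.3 restricts local albumin:globulin ratio and protein electrophoresis for the same reason. The central draw is therefore the main source of Ig values for the DSMB. Table 2 says the DSMB charter calls for adverse events to be related to observed Ig levels.

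For immunodeficiency, a person whom Table 2 says is barred could be enrolled with no eligibility deviation recorded. The drug is expected to lower all three Ig classes. Section 2.2 reports falls of up to 70% in IgA, up to 30% in mean IgG and up to 80% in mean IgM after single doses in healthy volunteers, and here dosing is monthly for 12 months.

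**Working it through.** The plan gives no figure of its own to reproduce. The check is a cell count and a comparison of passages.

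**1. Month 7 Ig**

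- Columns in Table 1: Screening, Day 1 pre-infusion, Day 1 post-infusion, Day 8, Months 1 to 12, Month 15. That is 4 + 12 + 1 = 17.
- Ig row: 10 marks, one blank, 6 marks. 10 + 1 + 6 = 17 cells, so the row is complete. The blank is the 11th cell. The first four columns precede Month 1, so 11 − 4 = 7, which is Month 7.
- Alignment check on other 17-cell rows: PK is blank only at Screening. Chemistry is blank only at Day 1 post-infusion and Day 8. The row "Study intervention infusion" is blank only at Screening, Day 1 post-infusion, Day 8, Month 12 and Month 15. These blanks fall where they should, so a shifted cell does not explain the Ig blank. PK, chemistry, infusion and APRIL are all marked at Month 7.
- Ig draws from Month 1 to Month 12: 12 − 1 = 11 of 12.
- Participants affected: Section 4.1 gives the total ("A total of 144 participants will be randomized with equal allocation (1:1:1:1) across the 4 intervention groups"). With the sub-study full, 144 − 60 = 84 have no Month 7 Ig draw (84/144 = 58.3%). If nobody joins, it is all 144.
- Length of the gap: Day 240 − Day 180 = 60 days, against 30 between adjacent monthly draws. With the ±7-day window at each end it runs from 60 − 14 = 46 to 60 + 14 = 74 days.

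Section 8.5 refers all participants to both Table 1 and Table 5, but only for VIS649 concentrations. It does not extend the Table 5 Ig column to everyone.

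**2. Primary immunodeficiency**

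Reading the 26 exclusions in Section 5.2 and the key exclusions in the synopsis, none names it. What reaches it indirectly:

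| Criterion | What it catches | What it leaves |
|---|---|---|
| Inclusion 6 | Low serum Ig. Table 2 puts selective IgA deficiency below the detection limit and CVID typically below 250 mg/dL IgG; the floors are 70 and 700 mg/dL | Deficiency with Ig above the floors, including cellular defects that serum Ig does not measure |
| Exclusion 7 | Earlier bone marrow or stem cell transplant | Anyone not transplanted |
| Exclusion 11 | Chronic infection, including chronic sinusitis and bronchiectasis, which Table 2 links to CVID | Anyone without chronic infection |
| Exclusion 13 | Acute infection at screening; no rescreening if an immunosuppressive condition predisposed to it | Anyone without acute infection at screening |
| Exclusion 24 | Any other illness the investigator considers to raise risk | Depends on judgment; not a prohibition |

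The iatrogenic half of Table 2's statement is matched by exclusion 8 and partly by 9 and 10. The primary half has no matching criterion.

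**The case against.** The strongest reply is that neither mismatch has a shown effect on safety or on any analysis.

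- Participant-level Ig is withheld from site and sponsor, and Section 7.1 has no Ig-based stopping rule. Ig therefore acts through five scheduled DSMB reviews and ad hoc ones, not through month-to-month decisions at the site.
- Section 4.2 expects full IgA suppression at 12 weeks, so Month 7 comes after several on-treatment values and one visit before the next. The protocol's Ig endpoints are at Months 9, 12 and 15.
- The deficiencies that Table 2 describes by Ig level are largely removed by the inclusion 6 floors, and Table 2's own statement can guide an investigator applying exclusion 24.
- The SAP cites a current protocol version with Month 16 follow-up and about 100 sites, where this protocol has Month 15 and about 80. A later version may already have changed the cell.

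Most of this stands, and it is why the practical effect is rated small. It does not remove the contradictions. A statement that testing is monthly is not met by 11 visits of 12, and a statement that a condition is prohibited is not met by a criterion that turns on opinion. Whether a later version resolves either point cannot be told from these documents.

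**Conclusion.** Both mismatches hold. Table 1 omits Ig at Month 7, contrary to Table 2 and out of step with Table 5, leaving at least 84 of 144 participants with one 60-day nominal gap. Section 5.2 has no criterion matching Table 2's bar on primary immunodeficiency. The people left to judgment alone are those with Ig above the floors and none of the listed conditions; the documents give no number, and it is probably small. Sample size, alpha and the primary analysis are untouched. On the analysis side, any Month 7 entry in the over-time Ig summaries of SAP 4.4.1.5 would rest on sub-study volunteers only, about 15 per group.

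A reader might infer more, and the documents do not support it:

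- That monthly Ig monitoring is absent. It is scheduled at 11 of 12 monthly visits, and at Screening, Day 1, Day 8 and Month 15.
- That the benefit-risk conclusion rests on these two items. Section 2.3.3 refers generally to precautions in the protocol, but the ones it names are the IgG enrollment threshold and DSMB review, and both are carried into the operative text.
- That anyone above the Ig floors is barred only through exclusion 24. Exclusions 7, 11 and 13 also bar some of them.
- That 84 participants are unprotected. The count is of missing samples, not of harm.

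This assumes that the Table 1 row was read correctly from the PDF, which should be confirmed against the original, and that the Table 5 Ig samples apply only to the sub-study, as Section 8.6 and footnote 13 indicate.

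**What to change.** Reconcile the Month 7 Ig cell of Table 1 with Table 2 and Table 5, so that all three describe the same schedule for the same participants. Reconcile Section 5.2, and the key exclusions in the synopsis, with Table 2's statement on primary immunodeficiency, so that the risk table and the eligibility list agree. The sponsor decides in each case which text governs.

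The cost is amendment wording. If the schedule is the part that changes, it adds at most one central Ig assay per participant, on blood already drawn at an existing infusion visit.

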2.3.2 Benefit Assessment

Immunoglobulin A nephropathy is a chronic disease with periodic flares. IgAN is a significant cause of chronic kidney disease (CKD) and ESRD, the clinical progression varies, with 30 – 40% of patients reaching ESRD 20 to 30 years after the first clinical presentation (Lai, Tang et al. 2016). These patients have significantly increased mortality and morbidity, with life expectancy reduced by 6 to 10 years when compared to healthy individuals. (Hastings, Bursac et al. 2017, Jarrick, Lundberg et al. 2019). There are currently no approved therapies for IgAN, and the current treatment strategies consist of 2 main aspects: nonspecific supportive treatments consisting of blood pressure control, treatment with ACEI/ARB, smoking cessation, lipid reduction, low-salt diet, or fish oil and immunosuppressive therapies such as steroids, cyclophosphamide, or azathioprine. The immunosuppressive therapies are usually employed in patients with a high risk of progression, as characterized by proteinuria > 1.0 g/d and declining GFR (Cheng, Zhang et al. 2009, Boyd, Cheung et al. 2012, KDIGO 2012, Radhakrishnan and Catran 2012, Barbour and Feehally 2017, Rodrigues, Haas et al. 2017). Recent trials have shown some benefit in proteinuria reduction with steroids in these patients, though they are at high risk for developing significant complications like infections, metabolic derangements, osteoporosis, and diabetes mellitus with these immunosuppressive agents; thus, limiting the duration for which these drugs can be given to patients despite benefit from a renal perspective (Pozzi, Andrulli et al. 2004, Rauen, Eitner et al. 2015, Tesar, Troyanov et al. 2015, Lv, Zhang et al. 2017). Hence, there is a critical need for a safe and specific treatment for IgAN.

VIS649 has the potential to provide a significant advancement in the therapeutic approach to IgAN. It has a very specific mechanism of action in the form of APRIL inhibition, which plays a critical pathophysiological role in the production of a-g IgA₁ in patients with IgAN.

VIS649 has an attractive safety profile based on currently available data, including data from the first-in-human study, Study VIS649-101, in which no SAEs attributable to VIS649 were observed. It is anticipated that VIS649 will be used as a chronic therapy and will significantly improve the outcomes in patients with IgAN when compared to intermittent therapies like steroids that are currently being used to treat these patients.

